4 OBJECTIVES AND ENDPOINTS

The objectives and endpoints for IM011054 are listed in Table 4-1.

Table 4-1: Objectives and Endpoints

Objective	Endpoint			
Primary				
To compare the efficacy of deucravacitinib to placebo in the treatment of participants with active PsA	Proportion of participants meeting ACR 20 response at Week 16			
Key Secondary				
To compare the efficacy of deucravacitinib to placebo at Week 16 as assessed by DAS28-CRP	Change from baseline in DAS28-CRP score at Week 16			
To compare the efficacy of deucravacitinib to placebo as assessed by HAQ-DI score at Week 16	Change from baseline in HAQ-DI score at Week 16			
To compare the efficacy of deucravacitinib to placebo as assessed by PASI 75 response at Week 16	Proportion of participants meeting PASI 75 response at Week 16, in participants with at least 3% BSA involvement AND at least sPGA 2 at baseline			
To compare the efficacy of deucravacitinib to placebo as assessed by SF-36 PCS score at Week 16	Change from baseline in the SF-36 PCS score at Week 16			
To compare the efficacy of deucravacitinib to placebo in enthesitis resolution at Week 16	Proportion of participants meeting enthesitis resolution (score of 0) among participants with enthesitis at baseline by LEI at Week 16			
To compare the efficacy of deucravacitinib to placebo in MDA response at Week 16	Proportion of participants meeting achievement of MDA where an MDA response is achievement of 5 of 7 following outcomes at Week 16: a) Tender joint count ≤ 1 b) Swollen joint count ≤ 1 c) PASI ≤ 1 or BSA ≤ 3% d) Patient assessment of PsA pain ≤ 15 e) Patient Global Assessment of PsA disease activity ≤ 20 f) HAQ-DI ≤ 0.5			
To compare the efficacy of deucravacitinib to placebo in FACIT-Fatigue score at Week 16	g) Tender enthesial points ≤ 1 Change from baseline in FACIT-Fatigue score at Week 16			

Table 4-1: Objectives and Endpoints

Objective	Endpoint
To compare the efficacy of deucravacitinib to placebo in dactylitis resolution at Week 16	Proportion of participants meeting dactylitis resolution at Week 16 among the participants with dactylitis at baseline, where resolution is defined as a tender dactylitis count of 0 in participants with a tender dactylitis count ≥ 1 at baseline
To compare the efficacy of deucravacitinib to placebo as assessed by structural damage at Week 16	Change from baseline in PsA-modified SvdH score at Week 16
Additional Secondary Objectives and Endpo	ints (At Each Time Point up to Week 16)

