To assess the efficacy of deucravacitinib (6 mg QD) to placebo as assessed by DAPSA score up to Week 16	 Change from baseline in DAPSA score Proportion of participants with achievement of DAPSA Low Disease Activity response Proportion of participants with 		
	achievement of DAPSA disease remission		
To assess the efficacy of deucravacitinib (6 mg QD) to placebo as measured by PGA-F up to Week 16	Proportion of participants meeting achievement of PGA-F of $0/1$ in participants with a baseline PGA-F score of ≥ 3		
To assess the efficacy of deucravacitinib (6 mg QD) to placebo up to Week 16 in	Change from baseline in DAS28-CRP score		
DAS28-CRP	Proportion of participants with achievement of a DAS28-CRP Low Disease Activity response		
	Proportion of participants with achievement of a DAS28-CRP disease remission		

Table 4-1: Objectives and Endpoints

Objective	Endpoint
To assess the efficacy of deucravacitinib (6 mg QD) to placebo as measured by the PASDAS up to Week 16	Change from baseline in PASDAS
To assess the efficacy of deucravacitinib (6 mg QD) in mCPDAI score up to Week 16	Change from baseline in mCPDAI score
To assess the efficacy of deucravacitinib (6 mg QD) to placebo as measured by the PsARC up to Week 16	Proportion of participants achieving PsARC, where participants must achieve improvement in 2 of 4 measures, 1 of which must be joint pain or swelling, without worsening in any measure
To assess the efficacy of deucravacitinib (6 mg QD) to placebo as measured by the BASDAI score up to Week 16	Proportion of participants meeting achievement of improvement from baseline in BASDAI score among participants with spondylitis in addition to peripheral joint involvement as their presentation of PsA
To assess inhibition of structural damage up to Week 16	 Proportion of participants meeting achievement of total PsA-modified SvdH score of ≤ 0, ≤ 0.5, and ≤ SDC at Week 16 Proportion of participants meeting achievement of PsA-modified SvdH erosion score change of ≤ 0, ≤ 0.5, and ≤ SDC at Week 16 Proportion of participants meeting achievement of PsA-modified SvdH JSN score change of ≤ 0, ≤ 0.5, and ≤ SDC at Week 16 Change in PsA-modified SvdH erosion score from baseline at Week 16 Change in PsA-modified SvdH JSN score at Week 16

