To assess the efficacy of deucravacitinib (6 mg QD) to placebo as measured by improvement in domain scales scores, PCS score, and MCS score of SF-36 up to Week 16	Change from baseline in domain scales scores, PCS score, and MCS score of SF-36

Table 4-1: Objectives and Endpoints

Objective	Endpoint
To assess the efficacy of deucravacitinib (6 mg QD) to placebo as measured by	Change from baseline in the subcomponents of the WPAI questionnaire
improvement in WPAI up to Week 16	1
To assess the efficacy of deucravacitinib	Change from baseline in the EQ-5D-5L utility
(6 mg QD) to placebo on general quality of	scores and its subcomponents
life up to Week 16	
To assess the efficacy of 6 mg deucravacitinib	Change from baseline in PROMIS sleep
QD to placebo on sleep disturbance score up	disturbance score (short form)
to Week 16	

Table 4-1: Objectives and Endpoints

[figure not shown]

Table 4-1: Objectives and Endpoints

[figure not shown]

Table 4-1: Objectives and Endpoints

[figure not shown]

Table 4-1: Objectives and Endpoints

Objective	Endpoint
Safety	
To assess the safety and tolerability of	Incidence of AEs, SAEs, AEs leading to
deucravacitinib in participants with active	discontinuation of treatment and study
PsA	discontinuation, ; change in
	laboratory, ECG, and vital signs; and abnormalities in laboratory, ECG, and vital
	signs

Table 4-1: Objectives and Endpoints

[figure not shown]

Table 4-1: Objectives and Endpoints

Objective	Endpoint
Abbreviations: ACR, American College of Rheumatolo	ogy; AE, adverse event;
BASDAI, Bath Ankylosing Spondylitis Disease Activity; DAPSA, Disease Activity Index for Psoriation	BSA, body surface area; Arthritis; DAS28-CRP, Disease Activity Score 28 with C-
reactive protein;	ECG, electrocardiogram; EQ-5D-5L, 5-level EuroQoL 5-ness Therapy; HAQ-DI, Health Assessment Questionnaire -
Disability Index; IL, interleukin	; JSN, joint space narrowing; LEI, Leeds Enthesitis Index;
disease activity;	Index; MCS, Mental Component Summary; MDA, minimal PASDAS, Psoriatic
	and Severity Index; PCS, Physical Component Summary; DMIS, Patient-Reported Outcome Measures Information
System; PsA, psoriatic arthritis; PsAID, Psoriatic Arthritic Criteria; QD, once daily; SAE, serious adverse event;	s Impact of Disease; PsARC, Psoriatic Arthritis Response
SDC, smallest detectable change; SF-36, Short Form-	-36; SPARCC, Spondyloarthritis Research Consortium of wdH, Sharp-van der Heijde; TH, T-helper; WPAI, Work

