6.1 Inclusion Criteria

1) Signed Written Informed Consent

a) Participants must be willing to participate in the study and sign the informed consent form (ICF).

2) Type of Participant and Target Disease Characteristics

- a) Participant has been diagnosed to have PsA (by any criteria) of at least 3 months, duration at Screening.
- b) Participant meets the Classification Criteria for Psoriatic Arthritis (see Appendix 5) at Screening.
- c) Participant has active plaque psoriatic skin lesion(s) or documented medical history of plaque PsO at Screening.
- d) Participant has active arthritis as shown by ≥ 3 swollen joints and ≥ 3 tender joints (66/68 joint counts) at Screening and Day 1.
- e) Participant has ≥ 1 PsA-related hand and/or foot joint erosion on X-ray during Screening Period that is confirmed by central reading.
- f) Participant has $hsCRP \ge 3 \text{ mg/L}$ at Screening.
- g) Participant has had documented inadequate response, loss of response, or intolerance to at least 1 of the following:
 - i) A csDMARD (MTX, SSZ, LEF, or hydroxychloroquine [HCQ]) maximally tolerated dose, and/or apremilast, after a minimum of 12 weeks, duration of therapy given for the treatment of PsA.
 - ii) An NSAID after a minimum of 4 weeks, duration of therapy given for the treatment of PsA, or participant has intolerance to those treatments in the opinion of the investigator.
- h) Concurrent use of 1 csDMARD, and/or NSAID, and/or oral glucocorticoid is permitted but not required during the study.
 - i) If such treatment was administered, then participants must meet the following requirements:
 - (1) If on csDMARD (MTX, SSZ, LEF, hydroxychloroquine [HCQ]), the participant must have been on it for at least 12 weeks and be on a stable dose for at least 28 days prior to Day 1.
 - (a) If on MTX, the route of administration and dose must be stable and the dose must be ≤ 25 mg/week.
 - (b) If on SSZ, the dose must be ≤ 3 g/day.
 - (c) If on HCO, the dose must be < 400 mg/day.
 - (d) If on LEF, the dose must be ≤ 20 mg/day.

Note: If currently not on MTX, SSZ, or HCQ, the participant must have not received it for at least 28 days prior to Day 1. If currently not on LEF, the participant must not have received it for at least 12 weeks prior to Day 1.

- ii) If on NSAID, the participant must be on a stable dose for at least 14 days prior to Day 1.

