9.1.24 Imaging Assessment for the Study

Images will be submitted by the sites to a central imaging vendor for blinded independent central review. Prior to scanning the first participants, sites should be trained by the central imaging vendor to understand the image acquisition guidelines and submission process as outlined in the X-ray Imaging Manual provided by the central imaging vendor.

Any incidental findings of potential clinical relevance that are not directly associated with the objectives of the protocol should be evaluated and handled by the primary study investigator as per standard medical/clinical judgment.

Digital radiographic (X-ray) assessments of both hands	and both feet will be performed at
Screening, Week 16,	Visits as noted in the Schedule of
Activities. Visit windows are the following: Screening Visit	t within 28 days prior to first
investigational product treatment, Week 16 ± 5 days, Week	days, Week days, and
Week days of the scheduled visit, and ET \pm 5 days	s of the scheduled visit (if ET Visit is
after Week 8 of the Placebo-controlled Treatment Period or a	after Week 24 of the Active Treatment
Period).	

X-ray scans with technical issues identified at the investigator site or by the central imaging vendor should be repeated within 7 days of notification. Additional information is provided in a separate X-ray Imaging Manual provided by central imaging vendor.

Radiographic assessments will be performed according to the PsA-modified SvdH score. The evaluation of the X-ray scans will be performed centrally by 2 independent primary readers. An adjudication will be performed in case of significant discrepancy among the 2 readers. All readers will be blinded to clinical details and treatment. Central image evaluation methodology will be described in an Imaging Charter.

Participant eligibility must be confirmed by central review prior to randomization with regard to the presence of at least 1 PsA-related hand and/or foot joint erosion on the screening X-ray scans. The sites will be notified by the central imaging vendor on the outcome of the central eligibility assessments.

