10.3.1 Efficacy Analyses

Endpoint	Statistical Analysis Methods
Primary	The primary efficacy analysis model for the primary endpoint, ACR 20 response at Week 16 (responder/non-responder), will use a Cochran-Mantel-Haenszel test
	to compare the response rates of 6 mg deucravacitinib QD to placebo. The risk difference and odds ratio and the corresponding 2-sided 95% confidence interval will be provided.
	Non-responder imputation will be used at Week 16 for participants who have a missing ACR 20 response at Week 16 or who discontinued treatment (for any reason) prior to Week 16. The same imputation will be used for the analysis of this outcome at other time points.
	The primary estimand for the primary endpoint, ACR 20 response at Week 16, will be the treatment difference between deucravacitinib 6 mg QD and placebo in ACR 20 response at Week 16 for all randomized participants. The occurrence of the intercurrent event of study treatment discontinuation (for any reason) prior to Week 16 or a missing ACR 20 response at Week 16 will be considered as a measure of nonresponse to treatment at Week 16 if the participant would have continued on the study treatment up to Week 16. Non-responder imputation will be used for the above intercurrent event. Study treatment discontinuation is the only intercurrent event that will be accounted for in the primary estimand and a composite variable strategy is applied.
	Two sensitivity analyses using different imputation methods will be conducted for the primary endpoint at Week 16 to examine the impact of missing data.
	 A multiple imputation (MI) approach A tipping point approach
	A supportive analysis will be provided for the primary endpoint at Week 16, including all available efficacy measurement for all randomized participants. These available data will include efficacy measurements observed after study treatment discontinuation and efficacy measurements observed after switch to other treatments.
	Details will be given in the SAP.

Endpoint	Statistical Analysis Methods
Secondary	Binary Endpoints:
	Binary endpoints (other than ACR 20 response at Week 16) up to Week 16 will be analyzed using the same method as for the primary endpoint.
	Continuous Endpoints (except structural damage):
	Change from baseline at Week 16 will be analyzed using an analysis of covariance (ANCOVA) model. The model will include treatment, randomization stratification variables, and baseline value.

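### Table 4-1 applies the ≤ 0, ≤ 0.5 and ≤ SDC cuts to the total SvdH score itself, although the two sibling endpoints apply them to the score change

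*Combined protocol and SAP*

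**What the plan says.** Table 4-1 (Section 4) lists three responder-type endpoints for the additional secondary objective of inhibiting structural damage up to Week 16:

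- Total score: "Proportion of participants meeting achievement of total PsA-modified SvdH score of ≤ 0, ≤ 0.5, and ≤ SDC at Week 16"
- Erosion score: "Proportion of participants meeting achievement of PsA-modified SvdH erosion score change of ≤ 0, ≤ 0.5, and ≤ SDC at Week 16"
- Joint space narrowing (JSN) score: "Proportion of participants meeting achievement of PsA-modified SvdH JSN score change of ≤ 0, ≤ 0.5, and ≤ SDC at Week 16"

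The table's abbreviation list gives "SDC, smallest detectable change". The key secondary structural endpoint in the same table is worded on the change scale: "Change from baseline in PsA-modified SvdH score at Week 16".

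Two other places bear on the point. Inclusion criterion 2e (Section 6.1) reads: "Participant has ≥ 1 PsA-related hand and/or foot joint erosion on X-ray during Screening Period that is confirmed by central reading". Section 9.1.24 says of scoring: "The evaluation of the X-ray scans will be performed centrally by 2 independent primary readers". It adds adjudication for significant discrepancy and describes the eligibility read separately.

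**The concern.** The erosion and JSN bullets put the cuts on a change. The total-score bullet puts the same cuts on the score, with no mention of change or baseline. A smallest detectable change is a threshold for a difference between two readings and has no evident meaning as a ceiling on a score level. Nor does a Week 16 level address inhibition of damage, because it adds damage present at entry to damage accrued on study.

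A derivation that followed the text would class a participant with existing damage and no progression as a non-responder. A derivation that followed the likely intention would report a result that does not match the endpoint in the protocol. No legible text elsewhere corrects the bullet.

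**Working it through.** The plan gives no figure to reproduce here. The check compares the two rules directly.

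**Notation.** Let b be the baseline total, c the change to Week 16 and k the cut.

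- Rule as written: b + c ≤ k, which is the same as c ≤ k − b.
- Sibling rule: c ≤ k.

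The rules coincide only when b = 0. As written, the improvement required grows one for one with baseline damage. With k = 0, the score must fall by its whole baseline value: by 1 from a baseline of 1, by 10 from a baseline of 10. The sibling rule with k = 0 requires only that the score has not risen.

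**Illustration.** The documents give no baseline SvdH distribution, so b = 1, 2, 5, 10 and 20 are assumed values. The last four columns count how many of the five meet each cut.

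| c | Week 16 totals (b + c) | total ≤ 0 | total ≤ 0.5 | change ≤ 0 | change ≤ 0.5 |
|---|---|---|---|---|---|
| −0.5 | 0.5, 1.5, 4.5, 9.5, 19.5 | 0/5 | 1/5 | 5/5 | 5/5 |
| 0 | 1, 2, 5, 10, 20 | 0/5 | 0/5 | 5/5 | 5/5 |
| +0.5 | 1.5, 2.5, 5.5, 10.5, 20.5 | 0/5 | 0/5 | 0/5 | 5/5 |

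The middle row is the decisive one: with no progression, nobody responds under the written rule and everybody responds under the sibling rule.

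**Can anyone reach a total of ≤ 0?** Criterion 2e makes it rare but not impossible. Scoring is described separately from the eligibility read, so readers may disagree about a small erosion, and apparent healing can occur. For example, if readers are averaged and only one scores the erosion (an assumption), b = 0.5 and c = 0 give a total of 0.5, which fails ≤ 0 and meets ≤ 0.5. The documents give no rate for a total of ≤ 0. Over an assumed range of 0% to 2% of 325 participants per arm:

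- 0% × 325 = 0
- 1% × 325 = 3.25
- 2% × 325 = 6.5

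That is none to about 6 or 7 per arm.

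**The ≤ SDC cut.** As written it becomes b + c ≤ SDC. The documents give neither an SDC value nor a baseline distribution, so this proportion cannot be estimated.

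**Missing data.** Section 10.3.1 says that binary endpoints "up to Week 16 will be analyzed using the same method as for the primary endpoint", which brings in non-responder imputation for a missing result or for stopping treatment before Week 16. With the wording corrected, a participant without an increase would meet the ≤ 0 cut, subject to that rule.

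**The case against.** The strongest reply is that this is a dropped word and not a design decision. The SDC cut makes sense only for a change, the objective speaks of inhibition, and the key secondary endpoint uses change from baseline, so a competent programmer would supply the missing word. The last bullet in the row also omits the reference to baseline, which suggests loose drafting. The endpoint is one of many additional secondaries. Formal structural inference rests on the ANCOVA of change, and ACR 50 and ACR 70 are the only examples named as possible additions to the testing strategy. The operative derivation may be correct in the SAP, whose text was not supplied. The illustrative baselines and the 0% to 2% range come from outside the documents, and the protocol does not set out how the score is computed.

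Much of this stands. The intention is recoverable, the reach is small, and nothing shows that the SAP derivation is wrong. The numbers illustrate the problem and do not estimate its size. The conflict with the sibling bullets and with the meaning of SDC does not depend on them. What the reply does not answer is that Table 4-1 is where the endpoint is defined, and the definition there is wrong on its face.

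**Conclusion.** The concern holds. The total-score responder endpoint is misdefined as written: its cuts sit on a level where the sibling endpoints, the meaning of SDC and the stated objective all call for a change. Taken literally, the ≤ 0 cut would be met by almost no one in either arm, and none of the three cuts would measure progression.

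The mismatch in wording is certain from the text. How few would reach ≤ 0 rests on the erosion entry criterion and on the assumed range above. The effect is limited to one additional secondary endpoint. The primary endpoint, the key secondary change in SvdH score, the sample size and Type I error control do not depend on it, and no loss of power is claimed. It should be corrected, but it does not threaten the trial's main conclusions.

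**What to change.** Reword the bullet along these lines: *Proportion of participants whose change from baseline to Week 16 in the total PsA-modified SvdH score is ≤ 0, ≤ 0.5 and ≤ SDC.* Then confirm that the SAP derivation for this endpoint uses the change from baseline. The cost is a few words in Table 4-1 and one check of the derivation. No assessment, sample size or testing rule needs to change.

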5 STUDY DESIGN

5.1 Overall Design

This is a Phase 3, 52-week, multi-center, randomized, double-blind, placebo-controlled study to evaluate the efficacy and safety of deucravacitinib versus placebo in participants with active PsA

who are naïve to biologic therapy.

Approximately 650 qualified participants will be randomized with equal allocation to receive either 6 mg deucravacitinib QD or matching placebo for an initial 16 weeks. All participants must have had a documented inadequate response, loss of response, or intolerance to at least 1 csDMARD, and/or apremilast, and/or NSAID given for the treatment of PsA. Participants will be allowed to continue on background medications (csDMARD, NSAID, and/or glucocorticoid) during the study as specified by the inclusion criteria. Participants must NOT have had prior treatment with a bDMARD or a JAK inhibitor for PsA and/or PsO.

[figure not shown]
- Screening Period (28 days)
- Treatment Period (52 weeks), comprised of
 - ◆ Placebo-controlled Treatment Period (16 weeks) (Week 0 to Week 16)
- Safety Follow-up Period (30 days) (following last dose of investigational product [IP] unless participant has continued in study for 30 days or more after discontinuation of IP)

Participants will undergo screening evaluations to determine eligibility within 28 days prior to administration of investigational product. Following the screening process, eligible participants will be randomized in a 1:1 ratio to 1 of the following 2 treatment groups:

- 1. 6 mg deucravacitinib QD
- 2. Placebo

At Week 16, participants originally randomized to placebo will be reallocated (in a blinded fashion for the initially randomized treatment) to receive 6 mg deucravacitinib QD through Week 52. Participants originally randomized to 6 mg deucravacitinib QD will continue to receive the same treatment and dose through Week 52.

[figure not shown]
Assessments for efficacy, safety, tolerability, quality of life, will be performed at specified time points as outlined in the Schedule of Activities (see Section 2).

Participants who discontinue study treatment will complete an Early Termination (ET) Visit, a Safety Follow-up Visit 30 days following the last dose of study treatment, and should complete each study visit through Week 52. Only participants who are lost to follow-up or withdraw consent will have no further study visits (see Section 8).

The study design schematic is presented in Figure 5.1-1.

Figure 5.1-1: Study Design Schematic

[figure not shown]

Abbreviations: N, number; QD, once daily.

5.1.1 Data Monitoring Committee

5.1.1.1 Data Monitoring Committee

An independent external DMC will be charged with monitoring accumulating data from the trial, as well as general aspects of trial conduct. The committee will meet periodically during the study to review aggregate analyses concerning efficacy and safety data from the trial. All members are selected with consideration for their respective expertise in the subject matter and/or in their experience in convening or participating in a DMC. Based on their overall benefit/risk evaluation, the DMC recommendations may include proceeding with the study per protocol, proceeding with the study with modifications, or study suspension. The scope, conduct, membership, processes, and accountabilities of the DMC are specified in the DMC Charter.

